### 9.4 Serious Adverse Event (SAE)

Adverse event that:

- a) led to a death.
- b) led to a serious deterioration in health that either:
- 1) resulted in a life-threatening illness or injury, or
- 2) resulted in a permanent impairment of a body structure or a body function, or
- 3) required in-patient hospitalization or prolongation of existing hospitalization, or
- 4) resulted in medical or surgical intervention to prevent life threatening illness or injury or permanent impairment to a body structure or a body function.
- c) led to fetal distress, fetal death or a congenital abnormality or birth defect.

NOTE 1: This includes device deficiencies that might have led to a serious adverse event if a) suitable action had not been taken or b) intervention had not been made or c) if circumstances had been less fortunate. These are handled under the SAE reporting system. NOTE 2: A planned hospitalization for pre-existing condition, or a procedure required by the Clinical Investigation Plan, without a serious deterioration in health, is not considered to be a serious adverse event.

### 9.5 Adverse Device Effect (ADE)

Adverse event related to the use of an investigational medical device.

NOTE 1- This includes any adverse event resulting from insufficiencies or inadequacies in the instructions for use, the deployment, the implantation, the installation, the operation, or any malfunction of the investigational medical device.

NOTE 2- This includes any event that is a result of a use error or intentional misuse.

### 9.6 Serious Adverse Device Effect (SADE)

Adverse device effect that has resulted in any of the consequences characteristic of a serious adverse event.

Version 6.0 Page 25 of 47

### 9.7 Unanticipated Serious Adverse Device Effect (USADE)

Serious adverse device effect which by its nature, incidence, severity or outcome has not been identified in the current version of the risk analysis report.

NOTE: Anticipated: an effect which by its nature, incidence, severity or outcome has been previously identified in the risk analysis report

### 9.8 Device deficiency

Inadequacy of a medical device related to its identity, quality, durability, reliability, safety or performance, such as malfunction, misuse or use error and inadequate labelling.

Version 6.0 Page 26 of 47

### 9.9 Assessment of Adverse Events

Each adverse event should be assessed according to the categorization charts for Adverse Events and Device deficiencies (from ISO 14155).

[figure not shown]

Figure 2: Adverse event categorization chart (from ISO 14155)

Version 6.0 Page 27 of 47

[figure not shown]

Figure 3: Device deficiency categorization chart (from ISO 14155)

### 9.10 Severity of Adverse Events

Each adverse event should be assessed for its severity, or the intensity of an event experienced by a subject, using the following:

- Mild discomfort noticed, but no disruption in daily activities
- Moderate discomfort sufficient enough to reduce or affect normal daily activity
- Severe Inability to work or perform normal daily activity

#### 9.11 AE Reporting

In case of an occurrence of an AE an AE Form in the CRF must be filled out within reasonable time. Occurred AEs must be addressed at the next monitoring visit. An annual safety report should be created and send to the EC by the Sponsor.

### 9.12 SAE Reporting

If an SAE bears an imminent risk of death, serious injury, or serious illness and that requires prompt remedial action for other patients/subjects, users or other it has to be reported immediately (max. 2 days).

Any other reportable event related to the medical device under investigation or due to study related procedures must be reported within 7 days.

All SAEs must be reported via the SAE reporting form (which will be provided by the Sponsor) according to MEDDEV 2.7/3 (Dec. 2010).

The investigator should notify the Sponsor within 24 hours of first learning of the serious adverse event.

Version 6.0 Page 28 of 47

Contact address:

Clinical Research, Institut Straumann AG

[contact] [contact]

The monitor may be required to collect further information for a final evaluation of the event. While the Sponsor is responsible for interactions with Health Authorities and Ethics Committees, it is the duty of the local investigator to keep the Sponsor informed.

It is recognized that in many cases SAEs will be treated in a medical rather than a dental environment and the investigator may not have immediate knowledge of the event. Close contact to the subjects should help to get relevant information in a timely manner. The investigator should report any SAE as soon as he has knowledge of the event within the above time frame irrespective of when the actual event occurred.

### 9.13 Monitoring / Follow-up of Subjects with Adverse Events

Any AE that occurs in the course of this study must be monitored and followed up until one or more of the following have occurred:

- The AE is resolved.
- Pathological laboratory findings have returned to normal
- Steady state has been achieved

It is the responsibility of the Sponsor to cooperate with the Investigator to assure that any necessary additional therapeutic measure and follow-up procedures are performed.

#### 9.14 Pregnancy

If a female subject becomes pregnant during the course of the study, the study visits should be completed as scheduled. Any study assessments that could potentially interfere with the pregnancy should be avoided until after the pregnancy (e.g. CBCTs, radiographs, etc.). The pregnancy should be recorded as an adverse event, whereas the start of pregnancy will be recorded as the start date of the AE and the date of child birth will be recorded as the end date.

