### 4.3 Study Treatments

Before entering into the study, each subject has to sign an informed consent. A subject is enrolled if she/he meets all inclusion criteria and at the same time does not meet any exclusion criteria. Enrolled subjects will be scheduled for sinus elevation. At surgery subject eligibility will again be evaluated according to secondary exclusion criteria. Subjects who do not meet any secondary exclusion criteria are randomized to one of the following groups:

- a) Sinus floor elevation with Straumann® VivOss™
- b) Sinus floor elevation with Geistlich Bio-Oss®

After a healing time of 1-2 weeks, sutures are removed, and the wound healing is evaluated. After a healing time of 6 months, an intermediate osteotomy for the dental implant placement is done by means of a trephine burr in such a way that the biopsy is harvested at the same time. Dental implant placement will be completed according to the standard procedure of the clinic. After a healing time of 1-2 weeks, the sutures are removed and the wound healing is evaluated. 4 months after implant placement the implant is initially loaded and the survival as well as the success rate will be evaluated.

Version 6.0 Page 14 of 47

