### 6.1.3 Risks and Benefits of the Investigational Device and Clinical Investigation

The investigational and control devices used in this study are CE marked. The clinical procedures performed are standard procedures.

The risk analyses for the investigational devices were conducted according to ISO 14971.

It can be stated that the risk from the investigational devices is low and acceptable, and the identified risk hazards from the devices are justified when considered against the significant clinical benefits provided. The investigational devices raise no new questions for safety and effectiveness as compared to similar devices. The investigator follows the instructions for use recommended by the manufacturer.

The possible risks and discomforts that may be associated with participation in this study are no different than having the same procedure (Sinus floor augmentation and placement of dental implants in a 2 stage approach) done without participation in this study. The following risks and adverse events can occur:

- General risks that exist with surgical procedures in the oral cavity: Bleeding and bruising, pain and swelling after the surgical procedure. Infections in the soft and hard tissue, delayed healing, recession of the gum and/or bone, temporary or permanent nerve damage in the jaw, oro-sinus or oro-nasal fistulas and possible rejection are very rare.
- General risks that exist with a surgical procedure using barrier membranes and can therefore not be completely ruled out: soft tissue dehiscence (tissue damage), haematoma, pain, increased sensitivity and redness due to inflammation
- Gingival inflammation (oral hygiene dependent): Oral hygiene instructions are given and oral hygiene procedures performed to prevent gingival inflammation.
- The following are examples of complications that can generally occur with a surgical procedure in the oral cavity and can therefore not be completely ruled out:
  - Slight pain and tenderness the first days after surgery
  - Slight swelling and redness the first days after surgery
- Pregnancy during the study, in particular at surgery, and the use of x-rays / CBCTs during pregnancy constitutes an additional risk to the foetus. Therefore neither

Version 6.0 Page 17 of 47

pregnant women nor women who plan to become pregnant must take part in this study.

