### 7.2 Pregnancy Test

Women of childbearing potential (women who are not surgically sterile or postmenopausal defined as amenorrhea for >12 months) must perform a pregnancy test (urine based) during screening. The test result must be documented in the source data.

During the study it is recommended to use highly effective contraceptive method (failure rate less than 1% per year) such as injectable, combined oral contraceptives or hormonal intrauterine devices (IUDs).

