#### 7.6 Cone Beam CT

In order to perform radiographic measurements of the residual bone height a cone beam computed topography (CBCT) not older than 12 months should be available. Dental cone beam CT scan (CBCT) technique provides a 3-dimensional view of the area of interest and therefore offers sufficient information on sinus anatomy to plan for sinus floor elevation.

**7.7 Adverse Events** (please see section 9. Definitions of Adverse Events and Device deficiencies (from ISO 14155))

Any adverse event must be documented at each study visit until the end of the study.

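### The only scheduled pregnancy test is at screening, about six months before the visit 4 surgery, so no protocol step would detect an early, unrecognised pregnancy before that operation

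*Combined protocol and SAP*

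**What the plan says.** **Testing.** Section 7.2 states that women of childbearing potential "must perform a pregnancy test (urine based) during screening". The Schedule of Assessment agrees: its pregnancy test row has one mark, under visit 1. Section 7.2 recommends highly effective contraception during the study but does not require it.

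**Visit 4.** This visit is surgical. According to section 4.3, "an intermediate osteotomy for the dental implant placement is done by means of a trephine burr", the biopsy is taken in the same step, and the implant is then placed. The window is 6 months ± 7 days after sinus elevation.

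**Risk.** Section 6.1.3 states: "Pregnancy during the study, in particular at surgery, and the use of x-rays / CBCTs during pregnancy constitutes an additional risk to the foetus". It concludes that neither "pregnant women nor women who plan to become pregnant must take part in this study".

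**Pregnancy during the study.** Section 9.14 has three relevant rules:
- Visits: "If a female subject becomes pregnant during the course of the study, the study visits should be completed as scheduled".
- Assessments: "Any study assessments that could potentially interfere with the pregnancy should be avoided until after the pregnancy (e.g. CBCTs, radiographs, etc".
- Recording: "The pregnancy should be recorded as an adverse event". Section 7.7 adds: "Any adverse event must be documented at each study visit until the end of the study".

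**The concern.** Section 6.1.3 puts surgery and imaging side by side as sources of foetal risk. The entry test protects the first operation, because screening is at most 14 days before it. It cannot protect the second, because a test at visit 1 says nothing about a conception in the following six months. If the subject knows that she is pregnant, adverse event recording should bring it out at visit 3 or visit 4. If she does not yet know, nothing scheduled would reveal it before an operation that could be postponed.

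There is also a lesser point of wording. Section 9.14 first keeps visits on schedule and then gives only imaging as examples of what to avoid, although 6.1.3 names surgery as well. What is at stake is patient safety, not the validity of the primary comparison.

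**Working it through.** **1. Age of the only test at visit 4.** Inputs: screening 0 to 14 days before visit 2, and visit 4 at 6 months ± 7 days (Schedule of Assessment; section 8.1). Six months is taken as 183 days.
- Shortest: 183 − 7 + 0 = 176 days.
- Longest: 183 + 7 + 14 = 204 days.

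Taking six months as 182 or 184 days moves either end by one day.

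**2. Unrecognised pregnancies expected at visit 4.** The documents give neither the number of women of childbearing potential nor a pregnancy rate. Assumptions: 5 to 15 such women among the 50 subjects, 1% to 10% pregnancies per year, and 4 to 6 weeks during which a pregnancy goes unrecognised. Only the 1% has a source: it is the failure limit for the methods recommended in section 7.2.

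Expected number = women × yearly rate × unrecognised weeks / 52.
- Low: 5 × 0.01 × 4/52 = 0.004.
- High: 15 × 0.10 × 6/52 = 0.17. The Poisson probability of no case is then exp(−0.173) = 0.84.

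**3. All pregnancies between visits 2 and 4.** If every one led to deferral, this would bound the number of subjects lost. Expected number = women × yearly rate × 0.5 year.
- Low: 5 × 0.01 × 0.5 = 0.025.
- High: 15 × 0.10 × 0.5 = 0.75.

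The likely loss is therefore 0 or 1 subject.

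**4. Power cost of one lost subject.** The plan's own figure comes first. Section 10.3 gives 25 per group for a difference of 0.4, SD 0.5, two-sided 5% and 80% power. The normal approximation gives 2 × (1.960 + 0.842)² × 0.5² / 0.4² = 24.5, rounded up to 25, so the figure is reproduced. With the exact unpaired t-test:
- 25 vs 25: power 79.1%.
- 24 vs 25: power 78.3%.
- Difference: about 0.9 percentage points.

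**5. Existing safeguards, by situation.**

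| Safeguard | Pregnancy known to the subject | Early pregnancy not yet known |
|---|---|---|
| Current pregnancy excluded (5.2) | entry only | entry only |
| Women planning pregnancy barred (6.1.3) | unplanned pregnancy not covered | unplanned pregnancy not covered |
| Adverse events recorded at each visit (7.7, 9.14) | should capture it | cannot capture it |
| Interfering assessments avoided (9.14) | applies | not triggered |
| Withdrawal at the investigator's discretion (8.3) | available | not triggered |
| Appropriate treatment for safety when an adverse event occurs (12.1) | applies | not triggered |

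The first column is largely covered. The second has no safeguard that acts at visit 4.

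**The case against.** The strongest objection is that the protocol already protects pregnant subjects and that the remaining gap is close to nil. Much of this stands.

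A reader might infer that 9.14 tells centres to operate on a subject known to be pregnant, because visits stay on schedule and only imaging is named. The documents do not support that. The test in 9.14 is potential interference with the pregnancy, and its list of examples is open-ended. Keeping a visit is not the same as operating at it. Bone biopsy and implant placement are themselves rows in the Schedule of Assessment, so they can fairly be read as assessments to avoid. Section 6.1.3 supplies the judgement that surgery carries risk, and 12.1 requires appropriate treatment for the subject's safety once an adverse event occurs. Naming surgery in 9.14 is therefore a useful clarification, not the correction of an unsafe instruction.

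A reader might also infer that the primary analysis is at risk, or that a biopsy deferred for pregnancy needs its own analysis rule. That does not follow either. General rules exist for visit windows (8.1), deviations (8.6), replacement (8.4) and the per protocol set (10.4.1). The SAP is to be finalised after a data review meeting (section 10). For most likely 0 or 1 subject, these are enough.

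On size, the upper figure of 0.17 needs all three assumptions at their upper ends at once. The documents give no sensitivity for a urine test, so some of the earliest weeks may remain undetectable even with a repeat test. They also do not quantify the foetal risk of the visit 4 procedure. A centre may test under its own standard of care. These points limit the weight of the concern. They do not remove it, because the protocol does not require any check before the second operation.

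**Conclusion.** The point holds as a cheap safety improvement with a very low expected frequency. Followed exactly, the plan would let an early, unrecognised pregnancy reach deferrable surgery undetected, with the only scheduled test 176 to 204 days old. The expected number of such cases is about 0.004 to 0.17, so most likely none. That range rests on assumed numbers of women, pregnancy rates and unrecognised weeks; only the 1% rate comes from the protocol. The length of the gap depends only on the visit windows and on counting six months as 183 days. Known pregnancies are largely covered, and no harm to the primary endpoint or to power is claimed.

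**What to change.** Make one amendment with two parts.

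1. **Repeat test.** In section 7.2 and in the visit 4 column of the Schedule of Assessment, add a urine pregnancy test for women of childbearing potential before the visit 4 surgery. State that if it is positive, osteotomy, biopsy and implant placement are deferred and section 9.14 applies.
2. **Clarification.** In section 9.14, add the visit 4 osteotomy, bone biopsy and implant placement to the imaging examples.

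No special per protocol or replacement rule for deferred biopsies is needed.

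The text change is one sentence in 7.2, one mark in the schedule and one phrase in 9.14. The running cost is one urine test per woman of childbearing potential. A deferred biopsy would miss the 6 months ± 7 days window, so the statistical cost is the likely loss of 0 or 1 subject worked out above.

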#### 10 Statistical Procedures

The statistical analysis principles described below will be supplemented by a detailed statistical analysis plan (SAP) which will be written after the first patients have performed visit 2 and will be finalized, based on the findings of the data review meeting, before the database is locked.

#### 10.1 Statistical Analysis

The statistical analysis will be performed by an external partner.

Descriptive summary statistics will be computed for all parameters documented on the case report form (CRF). Quantitative parameters will be described by seven-point scales with mean, standard deviation, median, quartiles, minimum and maximum. For qualitative

Version 6.0 Page 29 of 47

variables absolute and relative frequencies will be given. All descriptions will be done separately for treatment groups and visits.

The data of both study centres will be pooled. Pooling is justified by applying a high degree of standardization of study procedures and investigator training.

### 10.2 Statistical Hypotheses

The primary endpoint of this study is the histological evaluation of the ratio of newly formed bone to residual bone graft in *Straumann*® *VivOss*™ compared to *Geistlich Bio-Oss*® at visit 4 (6 month ± 7 days, after sinus elevation).

In this study the following hypothesis will be tested

Straumann® VivOss™ combined with Bio-Gide shows a significantly higher ratio of newly formed bone to residual bone graft compared to Geistlich Bio-Oss® combined with GeistlichBio-Gide at visit 4 (6 month ± 7 days, after sinus elevation).

- T: Test Group
- C: Comparator Group

Testing for Superiority (based on the per protocol (PP) data set):

 $H_{0S}$ : T = C

 $H_{1S}$ :  $T \neq C$ 

 $H_{0S}$  is the null hypothesis, claiming that there is no difference in the true mean of ratio of newly formed bone to residual bone graft after 6 months between the test group and the negative control group

H1S is the alternative hypothesis claiming that the true mean change of ratio of newly formed bone to residual bone graft after 6 months is unequal in the two treatment groups; either higher or lower in the test group than in the negative control group.

- T is the true mean at 6 months of the ratio of newly formed bone to residual bone graft in the test group.
- C is the true mean at 6 months of the ratio of newly formed bone to residual bone graft in the control group.

The secondary efficacy variables in this clinical study are:

- Survival rate of study implants evaluated at visit 6 (initial implant loading)
- Success rate of study implants evaluated at visit 6 (initial implant loading)

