### 4 Study Design

### 4.1 Type and Design of Study

This is a prospective, randomized, controlled, open label study, conducted at two sites in Germany and Switzerland comparing two treatment groups.

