### 8 Study conduct

#### 8.1 Visit Windows

The goal should always be to keep the given time point of each visit. However the time windows given below are the limits to be kept to perform according to the protocol.

Visit 0	Visit 1	Visit 2	Visit 3	Visit 4	Visit 5	Visit 6
Informed Consent	Screening Visit	Sinus elevation (Baseline)	Wound healing assessment	Implant placement	Wound healing assessment	Initial implant loading
28-2 days before screening	14-0 days before Baseline	Day 0	Day 7-14	6 months ± 7 days	2 weeks after visit 4	4 months ± 1 month after visit 4

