#### 8.3 Subject Completion / Withdrawal

It is possible that a subject may withdraw from the study at any time without prejudice and will be offered an alternative treatment for his/her dental condition. Subjects will be advised of the need for the prescribed follow-up visits for their ongoing care, well-being, and collection of relevant study data. All subjects must agree to return to the clinic to complete these follow-up visits.

The investigator may withdraw any subject from the study in the case of:

- non-compliance with the protocol
- a serious adverse event or an adverse event, in the opinion of the investigator, which prevents the subject's further participation in the study.

If a subject is withdrawn from the study as outlined above, the subject must be followed for reporting of adverse events. Withdrawn subjects will be followed according to the standard of care at the study centre.

Version 6.0 Page 23 of 47

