### 8.4 Subject Replacement Policy

For any subject who for any reason drops out of the per-protocol population a new subject with a new number should be allocated if the recruitment period is ongoing.

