#### 8.6 Protocol Deviations

Deviations from the procedures established in the protocol are not permitted. If a deviation occurs, the study monitor must be contacted immediately. The deviation must be documented and investigated. A written statement from the investigator on whether the deviation will affect the integrity of the study will be required.

Any deviation from the protocol (including deviations of the visit dates) may jeopardise the study outcome. Non-compliance of the subjects as well as of the investigators may lead to the closure of the respective centre.

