### 10.4 Populations for Analysis

### 10.4.1 Per Protocol Set (PP)

Randomized subjects who terminated the study and in whom no major protocol violations have been observed.

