### 10.4.2 Full Analysis Set (FA)

This data set will include all randomized subjects who have received at least one study device and from whom at least one measurement of post randomization data is available. It will include subjects even with major protocol violations and premature termination. The FA Set includes the PP Set.

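### The only stated superiority test uses a per-protocol set whose two membership conditions are undefined, and the full analysis set is given no test

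*Combined protocol and SAP*

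**What the plan says.** Section 10.2 names one analysis set for the primary comparison: "Testing for Superiority (based on the per protocol (PP) data set".

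Section 10.4.1 defines that set as "Randomized subjects who terminated the study and in whom no major protocol violations have been observed". The protocol separates major from minor violations nowhere and does not say at which visit a subject counts as having terminated.

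Section 10.4.2 defines the FA set by receipt of a device and at least one measurement after randomisation, and adds: "It will include subjects even with major protocol violations and premature termination". No test, estimate or sensitivity analysis is attached to it. Sections 10.1, 10.3 and 10.4.5 name no analysis set.

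On design, 4.1 states: "This is a prospective, randomized, controlled, open label study". Section 10 leaves detail to an SAP that is finalised after a data review meeting and before database lock. That SAP is not in the supplied text, and the protocol does not say that the meeting is blind to arm or to histology.

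**The concern.** A superiority claim rests on the comparison that randomisation set up. The PP set narrows that comparison by conditions that are at least partly decided later, and here the protocol fixes neither of them.

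- **Terminated.** The contrast with premature termination in 10.4.2 suggests that completion is meant. But the study termination form is also used for screening failures (8.2) and for subjects lost to follow-up (8.5), and the visit is not stated. If it is visit 6, a subject whose primary endpoint was measured at visit 4 leaves the primary test by dropping out during the following 4 ± 1 months.
- **Major violation.** Section 8.1 says of the visit windows: "However the time windows given below are the limits to be kept to perform according to the protocol". It does not say whether a biopsy outside ± 7 days is a major breach.

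The effect depends on the kind of exclusion. Exclusions unrelated to outcome cost only power. Exclusions that act alike in both arms leave the difference about unbiased. Exclusions that differ by arm and relate to outcome bias it, for or against the test product.

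The protocol also expects PP status to be acted on during the trial: "For any subject who for any reason drops out of the per-protocol population a new subject with a new number should be allocated" (8.4), while recruitment is open. Planned recruitment is 3 months (4.4) and the biopsy comes at 6 months. If recruitment keeps to plan, exclusions that arise at or after visit 4 are not replaced.

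**Working it through.** **1. Where PP and FA differ for the primary endpoint.** The endpoint is measured once, at visit 4.

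| Subject | In FA test? | In PP test? |
|---|---|---|
| No evaluable visit 4 biopsy | No value to use | No value to use |
| Biopsy, no major violation, reaches visit 6 | Yes | Yes |
| Biopsy, major violation (undefined) | Yes | No |
| Biopsy, leaves between visits 4 and 6 | Yes | Depends on the meaning of terminated |

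Only the last two rows matter. The third can include eligibility breaches that predate randomisation as well as later conduct violations.

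**2. The plan's own figure (10.3).** Inputs: difference 0.4, SD 0.5, two-sided 5%, power 80%.

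n = 2(1.960 + 0.842)² × 0.5² / 0.4² = 24.5, so 25 per group, as stated.

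By noncentral t at 25 per group: noncentrality 0.4 / (0.5 × √(2/25)) = 2.828, 48 degrees of freedom, power 79.1%. This is the baseline below.

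**3. Illustration of selection.** The documents give no exclusion rate, so these patterns are assumptions: normal data, SD 0.5, 25 per arm, pooled two-sided t-test at 5%, and k subjects dropped at random from the lower 12 values of an arm (2,000,000 simulated trials per case).

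The shift can be checked by hand. In samples of 25 with SD 0.5, the lower 12 average about 0.402 below the arm's true mean (by simulation). Dropping k of them moves the arm mean by k × 0.402 / (25 − k):

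- k = 1: 0.402 / 24 = 0.017
- k = 2: 0.804 / 23 = 0.035
- k = 3: 1.206 / 22 = 0.055, which is 14% of 0.4

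With no true difference:

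| Dropped | Shift | False finding for test (nominal 2.5%) | Two-sided error (nominal 5%) |
|---|---|---|---|
| None | 0 | 2.5% | 5.0% |
| 1 to 3 fully at random | 0 | 2.5% | 5.0% |
| 3 per arm, both arms alike | 0 | 2.2% | 4.3% |
| 1, test arm only | +0.017 | 3.2% | 5.0% |
| 2, test arm only | +0.035 | 4.1% | 5.4% |
| 3, test arm only | +0.055 | 5.3% | 6.2% |
| 3, comparator arm only | −0.055 | 0.9% | 6.2% |

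With a true difference of 0.4 and the same selection in the comparator arm only, power is 74.9%, 70.0% and 64.2% for k = 1, 2 and 3. For k = 3, smaller numbers explain little of the fall: at 22 against 25 without selection, noncentrality is 0.4 / (0.5 × √(1/25 + 1/22)) = 2.737 and power is 76.4%. The remaining 12.2 points (76.4 − 64.2) come from selection.

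**The case against.** **The SAP may settle this.** Section 10 calls its content principles to be supplemented, and the care taken to define FA suggests that some use was intended. The SAP could list major violations and add an FA test. That stands as a limit: the point concerns the protocol as supplied, not every later document. But an SAP that follows 10.2 keeps PP primary, and it is finalised after a meeting not stated to be blind.

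**FA does not cure missing biopsies.** Section 8.3 says "The investigator may withdraw any subject from the study in the case of" non-compliance or certain adverse events. A reader might infer that the FA set would undo the effect of such withdrawals. Before visit 4 it would not, because those subjects have no biopsy in either set. Likewise, the fall in power from 79.1% at 25 per arm to 73.6% at 22 is not specific to PP when the cause is a missing biopsy.

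**The investigator does not decide PP membership.** Section 8.6 says: "A written statement from the investigator on whether the deviation will affect the integrity of the study will be required". A reader might infer that an unblinded investigator's judgement determines who is analysed. No section gives that statement this role, and 8.6 also requires contact with the monitor, documentation and investigation.

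**Larger error rates can be produced, but not from the documents.** If the 3 lowest test-arm values were dropped, the false-positive rate for the test product would be 13.0%. That needs exclusion exactly by histology result. No histology exists before visit 4, and samples are read centrally, labelled by patient number and position (7.14, 7.15). Reader blinding is not stated, so this is not full protection, but nothing supports selection that sharp.

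**Conclusion.** The point holds for the protocol as written. Its only stated confirmatory test uses a set with two undefined membership conditions, at least partly settled after randomisation in an open-label trial, and it can drop subjects whose primary endpoint was validly measured. The exposure is confined to subjects with an evaluable visit 4 biopsy who are excluded from PP.

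The actual bias cannot be computed. Under the assumed partial selection of 3 subjects in one arm, the shift is about 0.055 in either direction. The false-positive rate for the test product rises to about 5.3% (two-sided about 6.2%) if the test arm is affected. Power falls to about 64% if the comparator arm is affected. These figures rest on normality, SD 0.5, 25 per arm and the assumed pattern.

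A reader might infer that exclusions will differ by arm or favour the sponsor's product. Nothing in the documents shows that. The finding is that the stated primary analysis is unprotected if they do. It should be fixed before database lock.

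**What to change.** **In 10.2**, base the primary test on the FA set, analysed as randomised. Use every evaluable visit 4 biopsy from the study sinus, whether or not the subject reaches visit 6, and the backup biopsy of 7.9 where the first cannot be evaluated.

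**Sensitivity analyses:**

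- the PP set;
- the primary result without biopsies taken outside ± 7 days, shown beside the full result;
- a pre-stated missing-data analysis, for example a tipping-point analysis by arm, reported with the number of missing biopsies per arm.

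**In 10.4.1**, define completion for the histology endpoint as completion to visit 4. Fix the list of major violations and the PP membership before those who decide see histology by arm.

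**Cost.** Wording in two sections, a paragraph on missing biopsies and three sensitivity analyses. No new data, visits or subjects. Subjects who deviated may dilute the estimate slightly. Some biopsies outside the endpoint's stated window enter the primary test, which is a design choice that the with-and-without display only partly offsets. FA still has conditions of its own after randomisation, though weaker ones than PP, and it does not recover missing biopsies.
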